- Evidence of leakage (i.e., cracking/breakage of a port, connector, hemofilter cartridge or tubing).
- Any unforeseen malfunction that results in the need for discontinuation.

This trial is an early safety efficacy study but is not powered for statistical significance. Insights into a comparison of historical controls matched to SCD treated subjects will utilize the ppCRRT Registry to match for: etiology of AKI, co-morbidities, CRRT modality, dose and form of anticoagulant, adverse events. [10]

The ppCRRT Registry has data fields for the primary reason for CRRT, including AKI and its cause, as well as co-morbidities which will be matched for primary organ system involvement. The CRRT modality was evenly distributed between convective and diffusive modality, with 60% of the convective modalities provided as CVVH and 40% as CVVHDF. The anticoagulant protocol will be standardized with ACD-A/CaCl₂ and all centers

used the same protocol in ppCRRT Registry as outlined in this study protocol. Thus, the ppCRRT Registry dataset will be able to be matched to our study subject cohort. Also as noted above, subjects will be matched for age, size and PRISM II score.

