6.4 BASELINE PERIOD

The Baseline Period begins at enrollment and ends at the start of the SCD Treatment Period (when the subject starts treatment). The following information will be recorded as close to the start of the SCD Treatment Period as possible. Data from standard of care tests may be used as baseline data, as long as it is captured within the time frames noted.

- **Demographic Data**
 - a) Date of birth
 - b) Gender
 - c) Race/ethnicity
- **Hospitalization Data**
 - a) Hospital Admission Date
 - b) Hospital Admission Diagnosis
 - c) ICU Admission Date
 - d) ICU Admission Diagnosis
 - e) Medical History
- **Vital Signs/Physical Assessment (within 12 hours prior to the start of SCD Treatment Period unless otherwise indicated)**
 - Temperature
 - Blood Pressure and heart rate
 - Body weight at ICU admission
 - PRISM II Score
 - Physical Exam
 - Urine Output (previous 24 hours)
 - ICU percent fluid overload at CRRT initiation (Defined as [(Fluid In (liters) – Fluid Out (liters))/ICU admission weight (kg)] x 100% where Fluid In and Fluid Out are calculated from ICU admission to CRRT initiation.
- **Clinical Laboratory Tests (within 12 hours prior to the start of SCD Treatment Period)**
 - CBC with differential
 - BUN/Creatinine
 - Na, K, Cl, HCO₃, Ca, Mg, Ionized Ca, PO₄
 - ALT, AST, Bilirubin, ALP, Total Protein, Albumin, Glucose
- **Respiratory**
 - Status – Ventilator support (yes/no; date of intubation)
 - If on Vent: FiO₂
 - If on Vent with an arterial line: Arterial Blood Gas (12 hours prior to start of SCD Treatment Period)
 - If on Vent without an arterial line: Arterial Blood Gas (if available within 12 hours of start of Observation Period per standard of care)
 - ECMO Status (yes/no; date of cannulation)
- **Blood for Research**
 - Blood sample should be collected within 6 hours before the start of the SCD Treatment Period

- Blood sample will be sent to an outside laboratory for testing of biomarkers. The research laboratory is Innovative BioTherapies located at [name].
- **Other (Event-driven)**
 - Acknowledgement (yes/no) to critical medications, vasopressors, and blood products administered to the patient in the 24 hours prior to start of SCD Treatment Period
 - Adverse Events occurring since enrollment
 - Microbiology/culture data (within the last 72 hr.)

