9. SAFETY

9.1. ADVERSE EVENTS

An Adverse Event is any sign, symptom, illness, clinically significant abnormal laboratory value or other adverse medical event that appears for the first time or worsens in a subject during this clinical study, regardless of whether or not it is considered related to the device.

Anticipated adverse events that may occur during CRRT include:

- thrombocytopenia
- hypo- or hypernatremia
- hypo- or hyperkalemia
- hypo- or hypercalcemia
- hypo- or hyperglycemia
- other electrolyte imbalance
- air embolism
- hypotension
- hypertension
- hemolysis
- increased oxygenation requirements
- fatigue
- dyspnea
- muscle spasm
- myalgia
- nausea
- vomiting
- fluid imbalance
- leukopenia
- arrhythmias
- hypothermia
- hyperthermia
- lactic acidosis
- temporary decrease in cardiac output or cardiac index
- disruption of skin integrity
- paresthesia
- tetany
- altered mental status
- bleeding
- shock
- infection
- bacteremia
- laryngospasm
- seizure
- death

Anticipated AEs associated with the addition of SCD to CRRT include:

- neutropenia
- thrombocytopenia
- hypotension
- hypo- or hypercalcemia
- alkalosis
- clotting within the device
- leakage due to cracking or breakage

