9.2. SERIOUS ADVERSE EVENTS

Any Adverse Event, whether considered study-treatment related or not, which fits any of the criteria below, is considered a serious adverse event (SAE):

- Results in death
- Is life-threatening (meaning that the patient was at risk of death at the time of the event; this does not refer to an event which might have caused death if it had occurred in a more severe form)
- Requires in-patient hospitalization or prolongs the existing hospitalization
- Is a persistent disability/incapacity
- Is a congenital anomaly or birth defect
- Is considered an important medical event by the Principal Investigator (e.g., surgery, return to ICU, emergency procedures)

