9.7.2. TREATMENT PERIOD THROUGH END OF STUDY

All adverse events that occur from the time of SCD start will be recorded as follows:

- Serious Adverse Events (identified in **Section 9.2**) will be recorded until Day 60 after enrollment, death, or subject withdrawal of study consent, whichever occurs first.
- Non-serious adverse events will be recorded until end of 120 hours after the SCD Treatment Period ends, death, subject withdrawal of study consent or until ICU discharge, whichever occurs first.

Any serious adverse event (regardless of relationship to the

treatment) occurring from the time of enrollment through end of study must be reported to the CCC and DCC at Cincinnati Children's Hospital, within 24 hours of knowledge of the event.

Each clinical trial site will be supplied with written SAE reporting instructions, SAE reporting forms and contact information for reporting of serious adverse events.

For any AE that is ongoing at the time of the initial report, periodic follow-up information will be required until the adverse event is resolved or the patient is no longer in the study, whichever occurs first.

The Investigator is responsible for all adverse events reporting to the Institutional Review Board (IRB) according to the requirements of the IRB and for providing clinical trial monitors with all medical records needed to source-verify the adverse events.

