Besides the test of the hypothesis the study is focused on observable, empirical and laboratory determinations of subject safety while on the SCD. Previous human trials have been conducted on the SCD device and the protocol contains a review of AE and SAE data from all SCD human studies and findings from those studies contributed to constructing the investigative safety profile. Safety endpoint measures specified in the protocol include adverse events, laboratory safety parameters, vital signs, ventilation status and hemodynamic variables. Device integrity and performance measurements are also defined as are circumstances which demand premature termination of SCD treatment.

Prolonged exposure to the SCD is anticipated to result in superior outcomes, although as noted above, this pilot study is not designed to assess for efficacy. However, we understand that a minimum amount of exposure to the SCD will be required for an appropriate safety analysis and for making any inference regarding efficacy. The ppCRRT experience demonstrated that the majority of patients (201/370) received CRRT for 1 to 7 days and exhibited 65% survival (Symons et al CJASN 2007 Table7).

This trial is an early safety efficacy study but is not powered for statistical significance. Insights into a comparison of historical controls matched to SCD treated subjects will utilize the ppCRRT Registry to match for: etiology of AKI, co-morbidities, CRRT modality, dose and form of anticoagulant, adverse events. [10]

The ppCRRT Registry has data fields for the primary reason for CRRT, including AKI and its cause, as well as co-morbidities which will be matched for primary organ system involvement. The CRRT modality was evenly distributed between convective and diffusive modality, with 60% of the convective modalities provided as CVVH and 40% as CVVHDF. The anticoagulant protocol will be standardized with ACD-A/CaCl₂ and all centers used the same protocol in ppCRRT Registry as outlined in this study protocol. Thus, the ppCRRT Registry dataset will be able to be matched to our study subject cohort. Also as noted above, subjects will be matched for age, size and PRISM II score.

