The Prospective Pediatric CRRT (ppCRRT) database will be used as a control for the CRRT treatment related factors including: patient age, gender, primary cause of AKI, total treatment duration, CRRT modality (CVVH, CVVHD, CVVHDF), CRRT small solute clearance (ml/1.73m²/hour), baseline estimated GFR (using the original Schwartz formula, which was used in the ppCRRT), urine output in the 24 hours prior to CRRT initiation (ml/kg/hour), percent fluid overload at CRRT initiation based on admission ICU weight, vasoactive medication number at time of CRRT initiation and mean airway pressure at CRRT initiation.

An additional analysis will also evaluate patients who have achieved targeted iCa levels during 90% of treatment time and those who do not.

In summary this protocol meets all criteria necessary for clinical scientific inquiry related to a test of hypothesis in a well monitored environment focused on subject safety during the conduct of the study. Basic statistics will be performed on the data sets along with historical data comparisons and subjected to subset analysis where appropriate. The results will help to guide the design of a future pivotal study of this device.

The rational for therapy, study objectives and endpoints, design, inclusion and exclusion criteria are explicitly defined. Subject safety parameters are well documented including safety reporting, safety observations and assays, procedures for subject withdrawal and study discontinuation criteria along with monitoring device integrity and performance. Lastly, a review of all prior SCD human study safety data is included in the protocol for full disclosure to study investigators and the informed consent document includes a full description of all known and potential risks of the device treatment.

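### Matching ppCRRT controls on adverse events, and controlling for total treatment duration, conditions the historical comparison on post-treatment outcomes

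*Combined protocol and SAP*

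**What the plan says.** Section 3.2 says the comparison with historical controls "will utilize the ppCRRT Registry to match for: etiology of AKI, co-morbidities, CRRT modality, dose and form of anticoagulant, adverse events". Section 12 repeats the list, again ending "dose and form of anticoagulant, adverse events". The paragraph after each list adds age, size and PRISM II score as matching factors.

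Section 12 then names the factors for which the registry will be used as a control. They include "patient age, gender, primary cause of AKI, total treatment duration, CRRT modality (CVVH, CVVHD, CVVHDF"). The same sentence ends with "vasoactive medication number at time of CRRT initiation and mean airway pressure at CRRT initiation", and it also ties urine output and percent fluid overload to the start of CRRT. Total treatment duration has no such anchor.

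On timing, Section 9.7.2 states "All adverse events that occur from the time of SCD start will be recorded as follows", and Section 9.7.1 treats unrelated events before SCD as medical history. Section 6.4 does collect "Adverse Events occurring since enrollment" in the baseline period.

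On endpoint status, Section 3.2 lists adverse events as a safety endpoint measure and defines duration of renal support as an endpoint. The synopsis (Evaluation Plan) makes time on CRRT an additional endpoint. The outcomes to be compared with historical data are mortality and dialysis dependency (synopsis; Section 3.1).

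**The concern.** A historical control should resemble the treated child as that child was before treatment. Adverse events and total CRRT duration are largely determined afterwards, by the device, by the underlying illness, or by the outcome itself.

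Three problems follow:

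- Matching on a variable that the device changes removes whatever part of its effect passes through that variable.
- Matching on a variable that reflects both the device and unmeasured severity pairs children of different underlying risk. That can create a difference where none exists.
- Matching on an endpoint removes the comparison on that endpoint.

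What is at stake is the reading of the historical comparison. Section 3.1 writes it into the primary objective, and Section 12 says the results will help to guide a later pivotal study. The uncontrolled description of adverse events is not affected.

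**Working it through.** The plan gives no figure to reproduce, so the check is mainly of the text. Two illustrations follow.

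**1. Are the variables fixed before SCD starts?**

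- *Adverse events:* recording runs mainly from SCD start (Section 9.7.2). The baseline form captures some earlier events (Section 6.4), but nothing restricts the match to those.
- *Total treatment duration:* part of it can precede SCD, because some children may already be on CRRT (Section 6.3, footnote 5). The total is known only when treatment ends.

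**2. Do they overlap with the outcomes compared?**

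- *Adverse events:* the Section 9.1 list headed "Anticipated adverse events that may occur during CRRT include" includes death, and the first seriousness criterion in Section 9.2 is "Results in death". In the limiting case of an exact match on all adverse events, fatal ones included, mortality would be equal in both groups by construction.
- *Duration:* under Section 7.2, treatment can end because the kidney recovers or because the child dies. A short duration therefore mixes the best and the worst outcomes.

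**3. Illustration: duration**

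From Section 12, 201 of 370 registry patients (54.3%) had 1 to 7 days of CRRT, with 65% survival. Survival in the other 370 − 201 = 169 is not given.

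Assume:

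- survival s of 35% to 55% in those 169;
- a share q with 1 to 7 days under SCD of 64.3% to 85%. The lower end is 9/14, from the 5 of 14 in the earlier pediatric trial who needed the full 7 days (Section 1.2);
- an effect on mortality that runs only through duration.

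True mortality difference = −(q − 0.543) × (0.65 − s)

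| q | s = 35% | s = 45% | s = 55% |
|---|---|---|---|
| 64.3% | −3.0 points | −2.0 | −1.0 |
| 75% | −6.2 | −4.1 | −2.1 |
| 85% | −9.2 | −6.1 | −3.1 |

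After matching on duration group, every entry becomes 0.

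**4. Illustration: adverse events**

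Assume two equal severity classes with 20% and 60% mortality (40% overall), higher severity adding 1.5 to the log-odds of an adverse event, and no SCD effect on death.

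- *Event rate 30% in controls, 50% under SCD.* Control mortality is 49.8% with an event and 35.8% without. Matched control mortality = 0.5 × 49.8% + 0.5 × 35.8% = 42.8%. Apparent difference = 40.0 − 42.8 = −2.8 points.
- *Event rate 50% in controls, 30% under SCD.* Control mortality is 47.2% with an event and 32.8% without. Matched control mortality = 0.3 × 47.2% + 0.7 × 32.8% = 37.1%. Apparent difference = 40.0 − 37.1 = +2.9 points.
- *Equal rates.* The difference is 0.

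**5. Scale against sampling error**

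With n = 10, one death is 1/10 = 10 points. Exact (Clopper-Pearson) 95% intervals for assumed death counts:

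| Deaths | Interval |
|---|---|
| 3/10 | 6.7% to 65.2% |
| 4/10 | 12.2% to 73.8% |
| 5/10 | 18.7% to 81.3% |

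**The case against.** The strongest objection concerns duration. Saying that the registry is used as a control for treatment factors could mean matching, adjustment or plain description, and description causes no bias. No endpoint is called total treatment duration. The synopsis has time on CRRT, and Section 3.2 has duration of renal support up to the last dialysis, which is not quite the same. The hypothesis of shorter dialysis concerns maintenance dialysis, so it is not direct evidence of an expected effect on CRRT time. All of this stands as a qualification. It does not supply the missing restriction to pre-SCD values, and on either reading total treatment duration is settled after SCD starts.

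The adverse event item may be loose drafting, since the plan never says how events would be matched, unlike etiology, modality and anticoagulant. That is possible, but both sections say to match on it, and an analyst following the text would do so.

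Other listed factors also lack a time anchor: CRRT modality, small-solute clearance and anticoagulant dose. That is correct, and it is a reason for a general rule as well as the two deletions.

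Finally, the comparison is exploratory, unpowered and limited to 10 children, with no test or decision rule attached. That limits the consequence. It does not make the match list correct. More children would reduce random error but would not remove this bias.

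**Conclusion.** The concern holds. As written, the plan matches historical controls on one endpoint and lists another among its control factors. Both can be changed by the device or by the outcome. Confidence is highest for adverse events, where the instruction to match is explicit. For duration it depends on reading the control list as matching or adjustment.

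Neither the size nor the direction of the bias can be derived from the documents. The illustrations (1.0 to 9.2 points masked; about 3 points created in either direction) rest on assumed inputs and show only that both kinds of error can arise. They are small beside the sampling error at n = 10, but the documents cannot establish that this would be so in practice. This is a should-fix point because the error is avoidable, not because it would decide the result.

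**What to change.** - Delete adverse events from the match lists in Sections 3.2 and 12, and total treatment duration from the control list in Section 12.
- Add one sentence: matching or adjustment uses only variables measured before SCD start. Candidates already in the protocol are age, weight, PRISM II, primary cause of AKI, percent fluid overload at CRRT initiation and baseline vasopressor use. The sentence would also settle the other factors that have no time anchor.
- Report adverse events and time on CRRT as outcomes. Any descriptive comparison of duration with the registry can stay if labelled as such.
- Optional, if the registry holds the dates: a sensitivity analysis using controls alive and still on CRRT at the same time since CRRT start as the child's SCD start.

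The cost is a wording change in two sections and no new data collection for the main change. Fewer factors will be balanced. The optional analysis is extra work and depends on dated registry fields that the documents do not show.

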5. SELECTION OF PATIENT POPULATION

5.1 STUDY POPULATION

Up to 10 pediatric patients with a clinical diagnosis of AKI requiring CRRT will be enrolled in this study, in up to 7 Clinical Centers in the United States.

Pediatric patients with a body weight (BW) between ≥ 10 and ≤ 20 kg receiving care in the Intensive Care Units of each participating hospital will be screened daily and identified for participation in the trial.

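### The plan says the registry can be matched to the trial children, but gives two different factor lists (16 or 17 distinct factors), no matching method or priority order, and two factors that arise after treatment starts

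*Combined protocol and SAP*

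**What the plan says.** Section 5.1 sets the size: "Up to 10 pediatric patients with a clinical diagnosis of AKI requiring CRRT will be enrolled in this study", with body weight from 10 to 20 kg.

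Section 3.2, repeated in Section 12, says registry controls will be used "to match for: etiology of AKI, co-morbidities, CRRT modality, dose and form of anticoagulant, adverse events". It adds: "Also as noted above, subjects will be matched for age, size and PRISM II score". After noting that the registry holds the relevant data fields, describing its mix of modalities and asserting a common anticoagulant protocol, it concludes: "Thus, the ppCRRT Registry dataset will be able to be matched to our study subject cohort".

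Section 12 then gives a second list in different terms: "The Prospective Pediatric CRRT (ppCRRT) database will be used as a control for the CRRT treatment related factors including: patient age, gender", followed by primary cause of AKI, total treatment duration, modality, small solute clearance, baseline GFR, prior urine output, fluid overload, number of vasoactive drugs and mean airway pressure.

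The only registry size in the documents comes with the duration of CRRT: "The ppCRRT experience demonstrated that the majority of patients (201/370) received CRRT for 1 to 7 days". The number of registry children weighing 10-20 kg is not given. On method, Section 12 promises basic statistics, comparisons with historical data and subset analysis where appropriate. No matching algorithm, caliper, control-to-case ratio, order of priority or rule for unmatched children is stated.

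**The concern.** The choice of controls determines the control mortality and dialysis rates. If the listed factors cannot all be matched closely, some must be dropped or coarsened. With no priority order, that choice could be made after the outcomes of up to 10 open-label patients are known.

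The comparison is not incidental. Section 3.1 puts historical data into the primary objective, and the synopsis Evaluation Plan compares mortality and dialysis dependency with historical controls. Section 12 says the results will help design a pivotal study.

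Two listed factors are a problem at any sample size. Adverse events are a safety endpoint in Section 3.2. Total treatment duration is known only once treatment has ended; time on CRRT is an additional endpoint in the Evaluation Plan, and duration of renal support is a defined endpoint in Section 3.2. Matching on either makes the groups alike on something the device may affect.

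**Working it through.** The plan gives no expected number of matches, so there is no figure of its own to reproduce. The check is a count of factors and a feasibility calculation under stated assumptions.

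**1. Counting factors.**
- List 1 (Sections 3.2 and 12, called matching): cause of AKI, co-morbidities, modality, anticoagulant dose, anticoagulant form, adverse events, age, size, PRISM II. That is 9, or 8 if anticoagulant dose and form are one item.
- List 2 (Section 12, called control): 11 factors.
- Shared: age, cause of AKI, modality, so 3.
- Distinct: 9 + 11 − 3 = 17, or 8 + 11 − 3 = 16.

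**2. Expected exact matches per child.** Let N be the pool, k the number of factors and q the chance that a registry patient agrees with a given child on one factor, treated as equal and independent across factors. Then expected matches are E = N·q^k, and the chance of at least one is P = 1 − (1 − q^k)^N. The value of q is an assumption, shown from 0.5 to 0.8. N = 370 takes the whole registry figure as the pool, which the documents do not say it is.

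| q | E, k = 9 | P, k = 9 | E, k = 17 | P, k = 17 |
|---|---|---|---|---|
| 0.5 | 0.72 | 0.51 | 0.003 | 0.003 |
| 0.6 | 3.7 | 0.98 | 0.06 | 0.06 |
| 0.7 | 14.9 | >0.99 | 0.86 | 0.58 |
| 0.8 | 49.7 | >0.99 | 8.3 | >0.99 |

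For example, 370 × 0.5^9 = 370/512 = 0.72. Counting list 1 as 8 factors gives 370/256 = 1.45 and P = 0.76 at q = 0.5.

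One factor can be anchored in the documents. The registry was half diffusive, and its convective half was 60% CVVH and 40% CVVHDF, so the split is 0.5, 0.3 and 0.2. If the trial has the same mix, chance agreement on modality is 0.25 + 0.09 + 0.04 = 0.38.

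**3. Weight band.** Restricting the pool to 10-20 kg uses up the size factor, leaving 8 and 16 factors. The share of the registry in the band is an assumption.

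| Share (N) | 8 factors, q = 0.5 to 0.8 | 16 factors, q = 0.5 to 0.8 |
|---|---|---|
| 10% (37) | 0.14 to 6.2 | 0.0006 to 1.0 |
| 25% (92) | 0.36 to 15.4 | 0.0014 to 2.6 |
| 50% (185) | 0.72 to 31.0 | 0.0028 to 5.2 |

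Each entry is N·q^k; for example, 92/256 = 0.36.

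**4. Correlated factors.** Exact matching of 10 children to 370 patients was simulated with assumed correlation between factors from 0 to 0.5 (150 runs per setting). The mean number of children with at least one match was:

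| Factors | Split in two | Split in three |
|---|---|---|
| 9 | 5.0 to 6.5 of 10 | 0.2 to 2.0 of 10 |
| 17 | 0.05 to 2.2 of 10 | 0 to 0.5 of 10 |

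**5. Score matching.** A propensity model with 17 covariates, 10 treated and 370 controls, with no true group differences, showed complete separation in 0 of 100 simulated runs. Such a method can therefore return a control for each child. It would be heavily overfitted, at 10/17 = 0.6 treated children per covariate.

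**6. The anticoagulant premise.** Sections 3.2 and 12 support the feasibility claim partly by saying that the trial and the registry share one standardized protocol. Section 6.2.1 lets each site use its own citrate protocol. These passages must be reconciled.

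**The case against.** A reader might infer that the lists cannot yield matches at all. The documents do not support that. Only list 1 is called matching, and even at 50% agreement its 8-factor reading gives each child about a 76% chance of at least one exact match in 370. At 80% agreement nearly every child has a match even on 17 factors. No exact method is stated, and score or distance matching would return a control for every child. Section 3.2 also coarsens one factor, since co-morbidities are matched only by primary organ system.

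A reader might also take all 17 as matching factors. Section 12 says the registry will be used as a control for list 2, which could mean adjustment or description. The 17-factor results apply only if the lists are combined for matching.

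Nor do the documents say that factors will be dropped after outcomes are seen; they only leave this open. The figure 370 is a denominator, not a stated pool. Independence is not a generous assumption either, since age tracks size. Finally, Section 3.2 says the trial is not powered, and Section 12 says it is not designed to assess efficacy.

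All of this stands, and it limits the size of the claim. It does not supply a method, reconcile the lists or make post-treatment factors suitable for matching. A returned control is also not necessarily a close one.

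**Conclusion.** The point holds as a gap in specification. The plan asserts feasibility without a method, a priority order or a count of eligible registry patients, over two lists that share three factors out of 16 or 17. Close joint matching of up to 10 children is doubtful on list 1 and unlikely on both lists together, unless factors are coarse or agreement is high.

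The numerical range is wide and rests on assumed agreement per factor, on independence (relaxed in the simulation) and on 370 as the pool. That width matters in itself: the outcome runs from almost no matches to nearly all, depending on choices the plan leaves open. Impossibility is not shown.

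The objection to matching on adverse events and total treatment duration needs none of these assumptions. The consequence is limited by the pilot purpose, but the comparison belongs to the primary objective in Section 3.1.

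**What to change.** In Sections 3.2 and 12, replace the feasibility statement and both lists with the following, fixed before outcomes are reviewed:

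- One short, ordered list of baseline factors, for example weight 10-20 kg, age, PRISM II, primary cause of AKI or sepsis, and fluid overload at CRRT start.
- Several registry controls per child selected on that list, with the method, caliper and ratio stated, and a rule for children without an acceptable match.
- A report of how many registry patients fall in the 10-20 kg band.
- A balance table showing the remaining baseline factors.
- Removal of adverse events and total treatment duration from the selection of controls.

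Reconcile the anticoagulant statements in Sections 3.2 and 12 with Section 6.2.1.

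The cost is a change of wording in the plan and a count from the registry. The downside is that imbalance on unmatched factors is shown, not removed.
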